Replace all previous version(s) of the protocol with this revised protocol and please provide a copy of this revised protocol to all study personnel under your supervision, and archive the previous versions.

DOCUMENT HISTORY

| Document | Date of Issue | Summary of Change |
|--------------------------|---------------|--|
| Revised Protocol 06 | 02-Jul-2019 | 
 Removed required number of participants in each special population subgroup Removed C1D1 physical exam from Table 2-2 Updated language to clarify that inhaled or topical steroids, and adrenal replacement steroid doses > 10 mg daily prednisone equivalent are allowed Updated treatment after the end of the study language to align with 2 year maximum treatment duration Added FACT-L collection during survival follow-up, which may be collected in office or over telephone |
| Administrative Letter 08 | 02-Oct-2018 | Updated Medical Director/Medical Monitor information |
| Revised Protocol 05 | 04-Jun-2018 | 
 Revised objectives and endpoints for Cohort C participants Updated sample size for Cohort C participants [REDACTED] Updated protocol to align with nivolumab program standards |
| Administrative Letter 07 | 26-Mar-2018 | 
 Updated study personnel Corrected errors in wording |
| Administrative Letter 06 | 28-Nov-2018 | 
 Corrected numbering Section 6.1.1 Inclusion Criteria for Cohort A1 Special Population |
| Revised Protocol 04 | 25-Oct-2017 | 
 Addition of Cohort C participants with high tumor mutation burden with subsequent addition of objectives, endpoints, tissue and blood collection, background, rationale, and analyses. Palliative radiotherapy language updated Maximum treatment duration of 24 months added. |
| Administrative Letter 05 | 31-Aug-2017 | 
 Updated study personnel and study title |
| Revised Protocol 03 | 27-Jul-2017 | 
Revised protocol 03 incorporates language from previous revised protocols, amendments, and administrative letters. These changes include updating the revised protocol with:
 
 Optional special population Cohort A1 [REDACTED] BMS standard days for study follow-up Change in title to reflect secondary endpoints New study personnel added 
Typographical errors were corrected for clarity.
 |
| Administrative Letter 04 | 12-Apr-2017 | 
 Updated study personnel and study title Clarified metagenomic analyses |
| Revised Protocol 02 | 09-Nov-2016 | Incorporates Amendment 04 |
| Amendment 04 | 09-Nov-2016 | Added a cohort of 400 participants (Cohort B, second-line non-small cell lung cancer [NSCLC]) who will receive nivolumab plus ipilimumab. |

| Document | Date of Issue | Summary of Change |
|---------------------|----------------------|---|
| | | Added specific exclusion criteria for patients with known epidermal growth factor receptor (EGFR) mutations or anaplastic lymphoma kinase (ALK) translocations sensitive to available targeted inhibitor therapy. |
| Revised Protocol 01 | 15-Sep-2016 | Incorporates Amendment 03 |
| Amendment 03 | 15-Sep-2016 | Management algorithms updated per revised nivolumab IB |
| Original Protocol | 22-Jun-2016 | Not Applicable |

OVERALL RATIONALE FOR THE REVISED PROTOCOL 06

[figure not shown]
The revised protocol removes the required number of participants in special population subgroups and collects FACT-L during survival follow-up. Additional changes were made to align protocol with program standards.

| SUMMARY OF KEY CHANGES OF REVISED PROTOCOL 06 | | |
|--|--|---|
| Section Number & Title | Description of Change | Brief Rationale |
| Section 5.2.1 All Cohorts (NSCLC) | Removed required number of participants for each special population subgroup | Required number of participants for each special population was removed because of limited accrual. |
| Table 2-2: Treatment Phase Assessments (CA209817) | Removed physical exam at C1D1 | Physical exam occurs at screening and does not need to be repeated at C1D1. |
| Table 2-3: Follow-up and Survival Procedures (CA209817) | FACT-L assessments may be administered in office or over the telephone. | FACT-L may be performed over the phone if office visit is not required for other assessments. |
| Section 7.7.2 Other Restrictions and Precautions | Updated language to clarify that inhaled or topical steroids, and adrenal replacement steroid doses > 10 mg daily prednisone equivalent are allowed. | Language updated to align with current program standards. |
| Section 7.8 Treatment After the End of the Study | Updated treatment after the end of the study | Updated treatment after the end of the study to align language with 2 year maximum treatment duration |

1 SYNOPSIS

Clinical Protocol CA209817

Protocol Title: A Phase 3b/4 Safety Trial of Flat Dose Nivolumab in Combination with Ipilimumab in Participants with Non-Small Cell Lung Cancer

Study Phase:

Phase 3b/4

Rationale:

Given the promising efficacy data observed with combined programmed death-1 (PD-1) and cytotoxic T lymphocyte-associated antigen 4 (CTLA-4) blockade, and the expected logistical benefits of flat nivolumab dosing, a need was identified to characterize the safety of nivolumab flat dosing in combination with weight-based ipilimumab administration. The combination will initially be studied as first-line (Cohort A) or second-line (Cohort B) therapy in Stage IV or recurrent non-small cell lung cancer (NSCLC), administered as nivolumab 240 mg every (q) 2 weeks plus ipilimumab 1 mg/kg q6 weeks. Additionally, Cohort C will assess the combination in first line NSCLC participants whose tumors harbor a high mutation burden.

An optional exploratory analyses and data generation will be conducted in separate special population (Cohort A1) participants with nivolumab flat dosing in combination with weight-based ipilimumab administration at participating sites. Typically, ECOG PS 2, renal and hepatic impaired patients, asymptomatic brain metastases, and HIV patients are excluded from NSCLC trials. Limited data is available in these subpopulations. This study will allow for additional safety data with nivolumab plus ipilimumab in these special populations at participating sites.

Study Population:

Participants with metastatic or recurrent NSCLC in Cohorts A, B, C, and optional A1 cohort.

[figure not shown]
Objectives and Endpoints:

| Objectives | Endpoints |
|---|--|
| 
Primary
 
 To characterize the safety of nivolumab administered as a flat dose in combination with weight-based ipilimumab dosing in Cohorts A, B, and C. | 
 The primary objective of the study will be assessed by summarizing the number and percentage of participants who experience high grade (Grade 3-4 and Grade 5) treatment-related select and immune-mediated adverse events (imAEs) in Cohorts A, B, and C, analyzed separately. The select AEs of interest are the following: pneumonitis, interstitial nephritis, diarrhea/colitis, hepatitis, rash, endocrinopathies, and hypersensitivity/infusion reaction events. |
| 
Secondary
 
To assess progression-free survival (PFS), overall survival (OS), duration of response (DOR) of nivolumab administered as a flat dose in combination with weight-based ipilimumab dosing in Cohorts A, B, and C.
 | 
 PFS defined as the time from first dosing date to the date of the first documented tumor progression, as determined by investigators (per Response Evaluation Criteria in Solid Tumors [RECIST] v1.1), or death due to any cause, whichever occurs first. OS defined as the time from first dosing date to the date of death. DOR defined as the time between the date of first confirmed response to the date of the first documented tumor progression (per RECIST 1.1), or death due to any cause, whichever occurs first |
| 
To assess the objective response rate (ORR) in Cohorts A, B, and C.
 | 
 ORR is defined as the number and percentage of participants with a best overall response (BOR) of confirmed complete response (CR) or partial response (PR). Best overall response (BOR) is defined as the best response designation, recorded |

| Objectives | Endpoints |
|--|---|
| | between the date of first dose and the date of the initial objectively documented tumor progression per RECIST v1.1 or the date of subsequent therapy, whichever occurs first. |
| To assess patient reported outcomes (PROs) in all treated participants | 
 • Patient reported outcomes (PROs): assessment of changes in disease-related symptoms and function dimensions of Health Related Quality of Life (HRQoL) using Functional Assessment of Cancer Therapy-Lung (FACT-L) |
| 
Exploratory
 
 • To characterize the pharmacokinetics, immunogenicity, ██████████ of nivolumab administered as a flat dose in combination with weight-based ipilimumab dosing. • To assess safety in the NSCLC special population cohort (A1) • To estimate the efficacy of nivolumab administered as a flat dose in combination with weight-based ipilimumab dosing in the NSCLC special population cohort (A1). • To assess the feasibility of prospective TMB testing in Cohort C | 
 • The pharmacokinetic (PK) objective will be measured from serum concentration. Samples will be collected to characterize the PK of nivolumab in combination with ipilimumab and to explore exposure-safety and exposure-efficacy relationships. • Exploratory immunogenicity ██████████ analyses will be performed. • Treatment-related select AEs, SAEs, and immune-mediated AEs in the NSCLC special population cohort. • Progression-free survival (PFS) • Objective Response Rate (ORR) • Overall survival (OS) • Duration of Response (DOR) • Participant reported outcomes (PROs) • Screen failure rate (Cohort C) |

Overall Design:

- Four cohort, open-label study of first-line (Cohort A), second-line (Cohort B), first-line special population (Cohort A1), and first-line high TMB (Cohort C) receiving nivolumab and ipilimumab treatment
- Participants will receive treatment with nivolumab 240 mg as a 30 minute infusion every 2 weeks and ipilimumab 1 mg/kg as a 30 minute infusion every 6 weeks, starting on Day 1, until progression, unacceptable toxicity, withdrawal of consent, 24 months of treatment from the first dose, or the study ends, whichever occurs first.
- Follow up data will be collected for up to 5 years. At the conclusion of the study, participants who are determined to be benefitting from study treatment may be eligible to continue receiving study drug as described in Section 7.8.

Number of Participants:

Approximately 500 participants are expected to be enrolled in each of the primary cohorts: Cohort A (first-line NSCLC) and Cohort B (second-line NSCLC) to achieve approximately 400 treated participants in each cohort.

An additional, special population of NSCLC patients, Cohort A1, will include approximately 200 treated participants. Site participation in Cohort A1 is optional.

For Cohort C (first-line NSCLC), an estimated 300 participants will be screened to achieve approximately 100 participants with high TMB. Participation in Cohort C will be limited to US sites due to the TMB processing being conducted at a single US-based facility.

Treatment Arms and Duration:

Study treatment:

| Study Drug for CA209817 | | |
|-------------------------|----------|--------------------------------------|
| Medication | Potency | Investigational Product (IP) /Non-IP |
| Nivolumab | 10 mg/ml | IP |
| Ipilimumab | 5 mg/ml | IP |

Participants in Cohort A (first-line NSCLC), Cohort B (second-line NSCLC), Cohort C (first-line NSCLC with high TMB), and special population cohort (A1) will receive treatment with nivolumab 240 mg as a 30 minute infusion every 2 weeks and ipilimumab 1 mg/kg as a 30 minute infusion every 6 weeks, starting on Day 1, until progression, unacceptable toxicity, withdrawal of consent, 24 months of treatment from first dose, or the study ends, whichever occurs first.

2 SCHEDULE OF ACTIVITIES

Table 2-1: Screening Procedural Outline (CA209817)

| Procedure | Screening Visit (≤ 42 days) | Notes |
|--|--------------------------------|---|
| Eligibility Assessments | | |
| Informed Consent | X | Informed Consent may be obtained within 42 days prior to first dose and initial IVRS call prior to any study specific procedure |
| Inclusion/Exclusion Criteria | X | Section 6 All inclusion/exclusion criteria should be assessed prior to first dose |
| Medical History | X | |
| Safety Assessments | | |
| Physical Measurements/Physical Examination | X | Include Height and Weight. Within 42 days prior to first dose |
| Vital Signs | X | Including BP, HR, & temperature. Obtain at the screening visit and within 72 hours prior to first dose. |
| Assessment of Baseline Signs and Symptoms | X | Assess within 14 days prior to first dose. |
| Serious Adverse Events (SAEs) | | Collected after signing the informed consent |
| Concomitant Medication Collection | X | Collect within 14 days prior to first dose through the study treatment period. |
| Pregnancy Test (WOCBP only) | X | Section 6.1 Within 24 hours prior to Day 1/Negative pregnancy test required at Screening. (An extension up to 72 hours prior to start of study drug may be permissible in situations where results cannot be obtained within the standard 24 hour window). |
| FSH Level | X | Post-menopausal females under age 55 years must have serum FSH level > 40 mIU to begin study treatment (Appendix 4). |

Table 2-1: Screening Procedural Outline (CA209817)

| Procedure | Screening Visit (≤ 42 days) | Notes |
|---|--------------------------------|---|
| Laboratory Tests | X | Section 9.4.2 CBC w/differential, Chemistry panel within 14 days prior to first dose. Hep B/C (HBV sAg, HCV antibody or HCV RNA), within 28 days prior to first dose. HIV test for all participants in Germany. |
| ECG (12-lead) | X | Section 9.4.1 Obtained only for participants who have met all eligibility criteria |
| Efficacy Assessments | | |
| Radiographic Tumor Assessments(chest, abdomen, pelvis, brain) | X | Section 9.1.1, Appendix 6 Performed within 28 days prior to first dose. CT with IV contrast of Chest, Abdomen, Pelvis and all known or suspected sites of disease should be imaged at the screening visit. MRI with gadolinium may be obtained if CT iodinated contrast is contraindicated. MRI of brain without and with gadolinium is required for all participants during screening to rule out brain metastases. CT of the brain (without and with contrast) can be performed if MRI is contraindicated. See Section 9.1 for further details |
| Biomarker Assessments | | |
| Archived Tumor Tissue or Recent Tumor Biopsy | X | Section 9.8.1 For Cohorts A, A1, and B: Fresh or archival sample, obtained within 12 months prior to enrollment. If archived slides are to be submitted, they must not have been cut > 6 months prior to submission, as sample may have degraded. One formalin-fixed paraffin embedded tumor tissue block or a minimum of 10 to 15 unstained tumor tissue sections are acceptable. For Cohort C: 
 • Fresh or archival sample, obtained within 3 months prior to enrollment. • Submission of 10 unstained tumor tissue sections for TMB testing by Foundation Medicine unless TMB results from Foundation Medicine is already available (Note: participants may not enter treatment phase unless known results are TMB high) Submission of 5 additional slides for PD-L1 testing if results are not already available from another BMS study, or a commercially available complementary diagnostic using an acceptable antibody (ie, 28-8, 22-C3, SP263). PD-L1 results obtained using antibody SP142 are not acceptable. |

Table 2-1: Screening Procedural Outline (CA209817)

| Procedure | Screening Visit (≤ 42 days) | Notes |
|--|--------------------------------|--|
| | | |
| EGFR Mutation and ALK Translocation Statuses | X | To be performed for all non-squamous participants (unless harboring known KRAS mutation). EGFR and ALK tests may be performed locally or at a central laboratory. May be performed outside the Screening period window, eg, > 42 days prior to first dose. |
| IVRS /Clinical Drug Supplies | | |
| IRT | X | Section 7.2 For participant number assignment at the time informed consent is obtained |

Table 2-2: Treatment Phase Assessments (CA209817)

| Procedure ^a | Cycle 1 Day 1 | Each Subsequent Cycle Day 1 (± 5 Days) | Day 15 and 29 of each Cycle (± 5 Days) | Notes For purposes of this table, a cycle refers to 6 weeks of treatment. |
|-----------------------------------|-------------------------------|--|--|--|
| Safety Assessments | | | | |
| Physical Measurements | X | X | | Include Height and Weight. |
| Targeted Physical Exam | | X | | |
| ECOG Performance Status | X | X | | See Appendix 5 |
| Vital Signs | X | X | | See Section 9.4 . Vital signs should be assessed at each on-study visit prior to dosing. |
| Adverse Event Assessments | Continuously during the study | | | Section 9.2 . SAEs should be approved within 5 days from entry. |
| Review of Concomitant Medications | X | X | | |
| Laboratory Tests | X | X | | Section 9.4.2 Within 72 hrs prior to dosing. Note: C1D1 labs do not need to be repeated if they were performed within 14 days of dosing. Creatinine clearance will be measured every 6 weeks for participants with renal impairment. |
| Pregnancy Test (WOCBP only) | X | X | | To be evaluated at least every 6 weeks. |

Table 2-2: Treatment Phase Assessments (CA209817)

| Procedure ^a | Cycle 1 Day 1 | Each Subsequent Cycle Day 1 (± 5 Days) | Day 15 and 29 of each Cycle (± 5 Days) | Notes For purposes of this table, a cycle refers to 6 weeks of treatment. |
|---|---|--|--|---|
| Efficacy Assessments | | | | |
| Radiographic Tumor Assessment (CT chest and known sites of disease. Repeat CT/MRI of abdomen with or without pelvis is required for participants with metastases in those areas at baseline, or if clinically indicated.) | 
Section 9.1 Tumor assessments should occur every 6 weeks (± 7 days) up to Week 48, then every 12 weeks until documented radiographic disease progression.
 
Participants with a history of known brain metastasis must have surveillance MRI study per standard of care (approximately every 12 weeks), or sooner if clinically indicated. CT of the brain without and with contrast can be performed if MRI is contraindicated. See Section 9.1 for further details.
 | | | |
| Patient Reported Outcomes | | | | |
| FACT-L | X | X | | 
The FACT-L will be administered on Day 1 for the first 3 Cycles (Cycle 1 Day 1, W6 and W12). Thereafter it will be administered every 2 Cycles (Weeks 24, 36, 48, etc).
 
On the day of study visits that include FACT-L assessment, the assessment will be performed PRIOR to any study procedures and treatment. Section 9.10
 |
| Pharmacokinetic (PK) and Immunogenicity Assessments | | | | |
| PK Samples | Throughout the study | | | Section 9.5.1 |
| Immunogenicity Samples | Throughout the study | | | Section 9.5.1 |
| | | | | |
| Clinical Drug Supplies | | | | |
| IRT Vial Assignment | X | X | X | Section 7.2 . Within 3 business days prior to dosing |
| Nivolumab 240 mg ^{b,c} | X | X | X | Section 7.1^c |
| Ipilimumab 1 mg/kg ^c | X | X | | Section 7.1^c |

- ^a If a dose is delayed, the procedures scheduled for that same time point should be delayed to coincide with when the time point's dosing actually occur (except radiographic tumor assessments).
- ^b Continues until disease progression, discontinuation due to unacceptable toxicity, 24 months of treatment, withdrawal of consent, or study closure.
- ^c Dosing window: nivolumab \pm 5 days unless dose frequency is less than 12 days and ipilimumab \pm 5 days unless dose frequency is less than 37 days)

Table 2-3: Follow-up and Survival Procedures (CA209817) - All participants

| Procedure | Follow-Up Visits 1 & 2 ^a | Survival Follow-up Visits ^b | Notes |
|---|-------------------------------------|--|---|
| Safety Assessments | | | |
| Targeted Physical Examination | X | | Section 9.4.1. To assess for potential late emergent study drug related issues. |
| Vital Signs | X | | Section 9.4 |
| Adverse Event Assessment | X | | Section 9.2. SAEs should be approved within 5 days from entry. Beyond 100 days from the last dose of study drug, participants will be followed for ongoing drug-related adverse events until resolved, return to baseline or deemed irreversible, or until lost to follow-up, withdrawal of study consent, or start of subsequent therapy. |
| Review of Concomitant Medications | X | | |
| Laboratory Tests | X | | Section 9.4.2. Required at Visit 1. Repeat at Visit 2 only if study drug related toxicity persists. |
| Pregnancy Test (WOCBP only) | X | | Section 9.2.5 |
| Patient Reported Outcomes | | | |
| FACT-L | X | X | For participants who have discontinued study therapy, but continue to be followed for radiographic progression per Section 9.1.1, the FACT-L must be collected at each visit. On the day of study visits that include FACT-L assessment, the assessment will be performed PRIOR to any study procedures and treatment. FACT-L assessments may be administered in office or over the telephone. Section 9.10 |

Table 2-3: Follow-up and Survival Procedures (CA209817) - All participants

| Procedure | Follow-Up Visits 1 & 2 ^a | Survival Follow-up Visits ^b | Notes |
|---|-------------------------------------|--|---|
| Efficacy Assessments | | | |
| Radiographic Tumor Assessment (CT chest and known sites of disease. Repeat CT/MRI of abdomen with or without pelvis is required for participants with metastases in those areas at baseline, or if clinically indicated.) | X | X* | Section 9.1.1. For participants who discontinue study treatment for reasons other than progressive disease, follow up scans should be performed every 6 weeks (± 1 wk) up to Week 48, then every 12 weeks until progressive disease, initiation of subsequent systemic therapy, lost to follow-up, or withdrawal of consent. *Radiographic assessments for participants who have not experienced progressive disease must be obtained every 6 weeks (± 7 days), and not delayed until follow-up visits 1 & 2. |
| Collection of Survival Status and Subsequent Therapy Information | X | X | Collect every 3 months in Survival Visits until death, lost to follow-up, or withdrawal of study consent. May be performed by phone contact or office visit. Additional subsequent cancer therapy details such as regimen, setting of the regimen, line of therapy, start date and end date of each regimen, best response to the regimen and date of progression after second line therapy will be collected. |

^a Follow-Up Visit 1 to occur 35 days from the last dose (± 7 days) or coinciding with the date of discontinuation of study drug (± 7 days) if the date of discontinuation is greater than 42 days from the last dose. Follow-Up Visit 2 to occur 80 days from Follow-Up Visit 1 (± 7 days) . Patients should be monitored continuously (at least up to 100 days after the last dose) as an adverse reaction with nivolumab or nivolumab in combination with ipilimumab may occur at any time during or after discontinuation of therapy.

^b Survival Follow-Up Visits to occur approximately every 3 months (± 14 days) from Follow-Up Visit 2.. Survival visit may be conducted in person or by telephone. BMS may request that survival data be collected on all treated participants outside of the 3 month specified window. At the time of this request, each participant will be contacted to determine their survival status unless the subject has withdrawn consent for all contact.

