7.4 Dosage Modification

7.4.1 Dose Delay Criteria for Cohorts A, B, and C

Nivolumab and ipilimumab administration should be delayed for the following:

- Grade 2 non-skin, drug-related AE, except for fatigue
- Grade 3 skin, drug-related AE
- Grade 2 drug-related creatinine, AST, ALT and/or total bilirubin abnormalities
- Grade ≥ 3 drug-related laboratory abnormality, with the following exceptions:
 - Grade 3 lymphopenia or asymptomatic amylase or lipase does not require a dose delay
 - Grade ≥ 3 AST, ALT, Total Bilirubin will require dose discontinuation
- Any AE, laboratory abnormality or inter-current illness which, in the judgment of the investigator, warrants delaying the dose of study medication.
- Participants receiving ipilimumab in combination with nivolumab that have drug-related toxicities that meet the criteria for dose delay, should have both drugs (ipilimumab and nivolumab) delayed until retreatment criteria are met. (Exceptions apply to the retreatment criteria after dose delay of ipilimumab and nivolumab for Grade 4 amylase and lipase abnormalities that are not associated with symptoms or clinical manifestations of pancreatitis and that are attributed to ipilimumab alone.)

Participants who require delay should be re-evaluated weekly or more frequently if clinically indicated and resume study medication dosing when re-treatment criteria are met.

Rescheduling:

- Nivolumab may be delayed until the next planned ipilimumab dose if the next ipilimumab dose is scheduled within the next 12 days. This will permit periodic ipilimumab dosing to be synchronized with nivolumab dosing.

- Ipilimumab should be dosed at the specified interval regardless of any delays in intervening nivolumab doses. However, in order to maintain periodic synchronized dosing of ipilimumab and nivolumab, the dosing days of nivolumab and ipilimumab may be adjusted within the permitted ± 5 day window, as long as consecutive nivolumab doses are given at least 12 days apart. Ipilimumab may be delayed beyond the 5 day window if needed to synchronize with the next nivolumab dose.
- If an ipilimumab dose is delayed beyond 6 weeks from the prior ipilimumab dose, then subsequent ipilimumab doses should be rescheduled to maintain the 6 week interval between consecutive ipilimumab doses.
- A dose delay of ipilimumab which results in no ipilimumab dosing for > 12 weeks requires ipilimumab discontinuation, with exceptions as noted in [Section 8.1.1.2](#).

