7.4.5 Criteria to Resume Dosing

7.4.5.1 Criteria to Resume Nivolumab for Cohorts A, B, and C

Participants may resume treatment with nivolumab when the drug-related AE(s) resolve(s) to Grade \leq 1 or baseline, with the following exceptions:

- Participants may resume treatment in the presence of Grade 2 fatigue.
- Participants who have not experienced a Grade 3 drug-related skin AE may resume treatment in the presence of Grade 2 skin toxicity.
- Participants with baseline Grade 1 AST/ALT or total bilirubin who require dose delays for reasons other than a 2-grade shift in AST/ALT or total bilirubin may resume treatment in the presence of Grade 2 AST/ALT OR total bilirubin.
- Participants with combined Grade 2 AST/ALT and total bilirubin values meeting discontinuation parameters ([Section 8.1](#)) should have treatment permanently discontinued.
- Drug-related pulmonary toxicity, diarrhea, or colitis must have resolved to baseline before treatment is resumed. Participants with persistent Grade 1 pneumonitis after completion of a

steroid taper over at least 1 month may be eligible for retreatment if discussed with and approved by the BMS Medical Monitor.

- Participants who received systemic corticosteroids for management of any drug-related toxicity must be off corticosteroids or have tapered down to an equivalent dose of prednisone ≤ 10 mg/day.

Participants with drug-related endocrinopathies adequately controlled with only physiologic hormone replacement may resume treatment after consultation with the BMS Medical Monitor (or designee). Adrenal insufficiency requires discontinuation regardless of control with hormone replacement.

Dose delay of nivolumab which results in treatment interruption of > 6 weeks requires treatment discontinuation, with exceptions as noted in [Section 8.1.1](#).

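### Table 2-2 footnote a ties a FACT-L due at a delayed Cycle Day 1 to the actual dosing day, so forms held up by toxicity are usually completed after improvement

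*Combined protocol and SAP*

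**What the plan says.** Footnote a of Table 2-2 (Section 2) is attached to the heading of the procedure column, so it governs every row. When a dose is delayed, "the procedures scheduled for that same time point should be delayed to coincide with when the time point's dosing actually occur". The one exception is given in brackets: "except radiographic tumor assessments".

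The FACT-L row of the same table reads "The FACT-L will be administered on Day 1 for the first 3 Cycles (Cycle 1 Day 1, W6 and W12"). It continues: "Thereafter it will be administered every 2 Cycles (Weeks 24, 36, 48, etc". On a visit day that includes the form, "the assessment will be performed PRIOR to any study procedures and treatment".

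Section 7.4.1 lists the reasons for delay in Cohorts A, B and C, among them "Grade 2 non-skin, drug-related AE, except for fatigue". A toxicity delay normally holds both drugs until the retreatment criteria are met. Section 7.4.5.1 then says "Participants may resume treatment with nivolumab when the drug-related AE(s) resolve(s) to Grade" 1 or lower, or baseline, with listed exceptions. Lung toxicity, diarrhea and colitis must be back at baseline. Section 7.4.5.2 has parallel rules for ipilimumab, and Cohort A1 follows the same framework with exceptions for organ impairment.

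After treatment stops, Table 2-3 collects FACT-L at the follow-up and survival visits and adds that "FACT-L assessments may be administered in office or over the telephone". Table 2-2 has no such sentence. Section 10.3.3.1 summarizes FACT-L descriptively at each assessment time point, states no rule for assigning late forms to a time point, and leaves further methodology to the SAP.

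**The concern.** Patient-reported outcomes are a named secondary objective, assessed as change in disease-related symptoms and function. If a form is due while a participant is in a toxicity delay, the footnote moves it to the day dosing restarts, and dosing restarts because the participant has improved. Whether and when the score is observed then depends on the state that it is meant to measure.

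Two consequences follow. Scores from the toxic period are never collected, so the time-point means tend toward the better state. Forms completed at different calendar times also share one nominal week. The second can be handled in analysis if actual dates are kept; the first cannot.

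**Working it through.** The plan states no precision or effect figure for FACT-L, so there is none to reproduce. The check is of the text, the schedule and the possible delay.

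**1. Does the footnote reach FACT-L?** Yes. The marker is on the column heading, FACT-L is a row of that table, and the only exception is imaging.

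**2. Which doses carry a form?** With 6-week cycles, week = 6 × (cycle − 1). Cycles 2, 3, 5, 7 and 9 give Weeks 6, 12, 24, 36 and 48, which matches the row. Day 15 and Day 29 doses carry no form.

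**3. What is the participant's state when the form is completed?**
- Grade 2 colitis or pneumonitis on the due date meets the delay criterion (Section 7.4.1).
- Dosing waits for return to baseline, apart from a case-by-case allowance for persistent Grade 1 pneumonitis (Section 7.4.5.1). Systemic steroids must be stopped or down to 10 mg/day prednisone equivalent or less.
- Meanwhile Section 7.4.1 asks for re-evaluation at least weekly. For delays beyond 6 weeks, Section 8.1.1.1 keeps tumor assessments and periodic safety and laboratory visits going. Neither names FACT-L.

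**4. How late can the form be?** Both limits run from the previous dose.
- Nivolumab: 6-week limit (Section 8.1.1.1) − 2-week interval = 4 weeks past plan, if the preceding Day 29 dose was on time.
- Ipilimumab: 12-week limit (Section 7.4.1) − 6-week interval = 6 weeks past plan.
- Listed exceptions, such as prolonged steroid tapers, allow longer. The footnote does not say which drug's dosing fixes the time point if the two restart on different days.

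**5. Does the shift carry forward?** Section 7.4.1 reschedules later ipilimumab doses to keep 6 weeks between them. If Cycle 2 Day 1 slips by 4 weeks, the form falls at 6 + 4 = Week 10. The forms labelled Weeks 12, 24, 36 and 48 then fall at Weeks 16, 28, 40 and 52, while imaging stays on calendar.

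**6. How large is the effect on a mean?** Shift = share of forms postponed by toxicity × score deficit missed. The documents give neither input, so both are assumptions:

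| Share postponed | 5 points | 10 points | 20 points |
|---|---|---|---|
| 5% | 0.25 | 0.5 | 1.0 |
| 10% | 0.5 | 1.0 | 2.0 |
| 20% | 1.0 | 2.0 | 4.0 |

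For scale, with an assumed SD of 15 to 25, the standard error SD/√n is 15/20 to 25/20 = 0.75 to 1.25 at n = 400 (Cohorts A and B) and 15/10 to 25/10 = 1.5 to 2.5 at n = 100 (Cohort C). Fewer forms at later visits would widen these. The shift could be smaller or larger than sampling error.

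**The case against.** Completing a questionnaire at pre-dose visits is a recognisable design choice, and here it serves a descriptive secondary endpoint with no comparator and no formal hypothesis. Several limits narrow its effect, and all of them stand:
- Only a delay that reaches a Day 1 visit with a form counts.
- The form comes first on its visit day, so a delay decided at that visit may leave a form already completed during toxicity. The plan does not say whether that form is kept or repeated.
- Grade 2 fatigue does not trigger a delay, and it and some Grade 2 skin toxicity may persist at resumption.
- Some delays have other causes, and some follow laboratory findings with no obvious effect on quality of life.
- Participants who discontinue are measured at Follow-Up Visit 1, by default 35 days (±7) after the last dose, whether or not toxicity has resolved.

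A reader might go further in ways the documents do not support. Active Grade 3 colitis or pneumonitis is not an example: Section 8.1.1.1 requires discontinuation, so no delayed dose remains for the footnote to act on. The 6- and 12-week limits are not lengths of delay past plan, since they run from the previous dose. The 33% Grade 3/4 treatment-related rate in the CA209012 q6-week cohort is the share ever affected, not the share in a delay at one visit. Multiplying it by a 15-point deficit (0.33 × 15 = 4.95) therefore gives no usable upper bound.

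None of this answers the central point. The footnote covers FACT-L, resumption generally requires improvement, and no form is required in between. The same footnote already protects imaging from dose-driven delay.

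**Conclusion.** The point holds as a modest one. For a participant in a toxicity delay on a FACT-L due date, the footnote usually places the form after improvement, so on-treatment means are likely biased toward better scores. The direction rests on one assumption: that FACT-L is lower during the toxicity than after it. The timing follows from the text: about 4 to 6 weeks late before the discontinuation limits apply, longer under exceptions, with later drift.

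The size is unknown. The 10% × 10 points = 1.0 point case is an illustration, not an estimate. A reader might infer that the trial understates the regimen's toxicity. The documents do not support that: adverse events are assessed continuously, so the primary safety endpoint is untouched. Nor is it right that no analysis could help. Using actual dates repairs the mixing of calendar times; only the scores never collected are lost.

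**What to change.** - **Footnote a:** extend the bracketed exception to *(except radiographic tumor assessments and FACT-L)*.
- **FACT-L row of Table 2-2:** replace the cycle-based wording with calendar weeks from first dose: baseline, Weeks 6, 12, 24, 36, 48 and so on, with a stated window (for example ±7 days, as for imaging), due even if dosing is delayed. The Day 1 and every-second-cycle wording has to go, because after a delay it would contradict the calendar weeks.
- **Mode:** allow telephone completion in Table 2-2 as Table 2-3 already does.
- **Section 10.3.3.1 or the SAP:** summarize FACT-L by actual assessment week. This also corrects the labelling of forms already collected late, though not the scores already missed.

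No dosing rule changes. The cost is a few words and an occasional call to participants who are already being re-evaluated at least weekly. The downside is that some on-treatment forms will be by telephone or away from a dosing visit, and the means may look slightly less favourable.
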